### **Detecting “BRCAness”**

One area of controversy is the best method for detecting “BRCAness” in tumor samples. Several efforts to identify a “BRCAness” signature have been reported using different methodologies including array comparative genomic hybridization (aCGH), quantitative real time- polymerase chain reaction (RT-PCR), multiplex ligation-dependent probe amplification (MPLA) and immunohistochemistry (IHC).

Techniques have been reported using frozen or formalin-fixed tumor tissue. As all the published studies have defined a “BRCA1 like signature” independently there is currently no standardized definition. Moreover, DNA or RNA based approaches require fresh frozen tissue for optimal results, expertise in those fields for interpretation (which is not readily available in non-academic setting) and significant time for tissue analysis and interpretation. Consequently, none of these methodologies are readily conducive for utilization by the clinician who is required to make time-sensitive treatment decisions. IHC can be rapidly translated into current clinical practice as both community

and academic pathologists utilize IHC on a routine basis from FFPE tissue and are competent in performing the assays and interpreting the results. Furthermore, IHC methods can be readily validated and replicated in standard clinical laboratories and added to the standard breast cancer diagnostic IHC panel (ER, PR, HER2, and Ki 67).

### **Preliminary data:**

In collaboration with the Tissue Core and Cellular/Molecular Analysis core (TACMASS) at the University of Arizona Cancer Center (UACC) we have validated a BRCA1 IHC assay in breast tumor samples. Antigen retrieval techniques and antibody titers have been optimized using the Genscript A00490 Rb polyclonal antibody. We retrospectively analyzed 45 breast tumor samples, 37 of which were triple negative tumors. Low BRCA1 protein expression was found in 43% of the triple negative tumors. This result is in concordance with other reported series of BRCA1 signatures using DNA and/or RNA based approaches. Clinical information was available in 37 patients. A total of 21 patients received anthracycline based chemotherapy of which 13 had intact BRCA1 and 8 had low BRCA1 protein expression. Fewer breast cancer recurrences were seen in patients with low BRCA1 protein expression (2/8) compared to those with intact BRCA1 protein expression (6/13). However, in this small sample of assessed tumors, chemotherapy was administered at different time points (neoadjuvantly or adjuvantly) and follow up was not standardized in all patients. Nevertheless, these results support our hypothesis that low BRCA1 protein expression predicts increased sensitivity to treatment with DNA damaging chemotherapy.

DNA damage leads to the early activation of BRCA1 where it plays a vital role in the homologous recombination (HR) repair of double stranded DNA. Unlike other mechanisms of DNA repair, BRCA1 mediated HR tends to be conservative and error free. Thus cells deficient in BRCA1 protein are uniquely susceptible to agents/mechanisms which cause DNA damage due to their inability to repair through HR. We propose to test the clinical utility of BRCA1 quantification by immunohistochemical (IHC) analysis for predicting response to chemotherapy in the prospective setting. Our **hypothesis** is that low BRCA1 protein expression in primary breast tumors of metastatic breast cancer patients predicts improved response to DNA damaging chemotherapy in the metastatic setting.

### **Methodology:**

**IHC staining for BRCA1:** Tumor samples will be reviewed to confirm adequate sample for staining. Tissues sections will be stained for BRCA1 by Genscript A00490 Rb polyclonal clone antibody using the Benchmark Ultra automated stainer (Ventana Medical Systems Inc, Tucson, Arizona). Low BRCA1 protein expression will be defined as  $\leq 5\%$  of cells staining with 1+ intensity of the tumor nucleus (i.e. nuclear long score  $\leq 5$ ). Intact BRCA1 protein expression will be defined as  $\geq 10\%$  of cells staining with 1+ intensity or  $\geq 5\%$  of cells staining with 2+ intensity of their nucleus (i.e. nuclear long score of  $\geq 10$ ). Nuclear long score of 6-9 i.e. 5-10% of cells staining with 1+ or  $< 5\%$  of cells stain with 2+ intensity, will be defined as indeterminate status.

**Quantitation of IHC:** Two Board Certified pathologists ([name], PhD and [name]) will evaluate each case using a semi quantitative histologic scoring method as previously described. Briefly, staining intensity for neoplastic cell's nucleus will be scored as: 0 negative, 1 weak, 2 moderate and 3 intense. In addition,

the percentage of positive neoplastic cells will be evaluated. The overall scores will be calculated by multiplying the intensity by the corresponding percentage of positive cells, resulting in a values ranging from 0 to 300. Low BRCA1 protein expression will be defined as nuclear long score of  $\leq 5$ , intact BRCA1 as nuclear long score of  $\geq 10$ , indeterminate BRCA1 expression as nuclear long score of 6-9.

**Chemotherapy agent:** Pegylated liposomal doxorubicin is frequently used in the salvage treatment of patients with metastatic breast cancer. It is a DNA damaging chemotherapy agent which has been reported to have a 25% overall response rate and 2.5 months median progression free survival in the salvage treatment of metastatic breast cancer. It has been shown to be safe in patients who have received prior anthracycline treatment.

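### The percentage wording for BRCA1 class does not match the nuclear long score it is said to equal, so tumours near the cut-offs fall into different or double classes

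*Combined protocol and SAP*

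**What the plan says.** Two paragraphs under Methodology in section 1.2 of the combined protocol and SAP define BRCA1 class.

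- **IHC staining for BRCA1** uses percentage and intensity, each with a score in explanation. Low is at most 5% "of cells staining with 1+ intensity of the tumor nucleus (i.e. nuclear long score" of at most 5). Intact is at least 10% at 1+, or at least 5% "of cells staining with 2+ intensity of their nucleus (i.e. nuclear long score of" at least 10). The indeterminate class is introduced as "Nuclear long score of 6-9 i.e. 5-10% of cells staining with 1+ or" fewer than 5% "of cells stain with 2+ intensity, will be defined as indeterminate status".
- **Quantitation of IHC** gives the formula: "The overall scores will be calculated by multiplying the intensity by the corresponding percentage of positive cells", with intensity graded 0 to 3 and a range of 0 to 300. It then restates the classes by score alone: low at 5 or less, intact at 10 or more, and "indeterminate BRCA1 expression as nuclear long score of 6-9".

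The score cut-offs are the same in both paragraphs. Neither paragraph says which wording prevails if score and percentage disagree.

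Section 8.1 uses the class to assign patients to the normal or low cohort, with an expected split of 35 to 15 among 50 patients. Section 8.2 adds that, if the normal arm closes, tumours will be analysed and only patients with low expression will be enrolled.

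**The concern.** The percentages are offered as another way of stating the score bands. If they are not, a pathologist who works from the percentages can reach a different class from one who calculates the score on the same tumour.

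BRCA1 class is the exposure in the primary objective. It determines who counts toward the low cohort of 15 and toward the 12 and 35 of the two-stage cohort. If the normal arm closes, it also decides whether a patient can be enrolled at all. A tumour called indeterminate has no named cohort in section 8.1, and 35 + 15 already accounts for all 50 patients. A disagreement between low and indeterminate is therefore a disagreement about whether the patient is in the primary analysis.

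**Working it through.** **Inputs**, all from Methodology in section 1.2: score = intensity x percentage of positive cells; score bands 5 or less, 6-9, and 10 or more; percentage rules as set out above. I take whole-number percentages and one staining intensity per tumour.

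**The plan's stated equivalence.** Scores of 6-9 are said to correspond to 5-10% at 1+ or fewer than 5% at 2+.

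- 1+ limb: 1 x 5 = 5 up to 1 x 10 = 10. The range is 5-10, not 6-9.
- 2+ limb: 2 x 1 = 2, 2 x 2 = 4, 2 x 3 = 6, 2 x 4 = 8. The scores are 2, 4, 6 and 8, and the first two lie below 6.

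The equivalence is not reproduced on either limb.

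**Both rules side by side.**

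| Staining | Score | Class by score | Class by percentage text |
|---|---|---|---|
| 1-4% at 1+ | 1-4 | low | low |
| 5% at 1+ | 5 | low | low and indeterminate |
| 6-9% at 1+ | 6-9 | indeterminate | indeterminate |
| 10% at 1+ | 10 | intact | intact and indeterminate |
| 11% or more at 1+ | 11 or more | intact | intact |
| 1% at 2+ | 2 | low | indeterminate |
| 2% at 2+ | 4 | low | indeterminate |
| 3-4% at 2+ | 6, 8 | indeterminate | indeterminate |
| 5% or more at 2+ | 10 or more | intact | intact |

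There are four conflicting values. At 1% and 2% at 2+ the two rules give different classes. At 5% and 10% at 1+ the percentage text places one tumour in two classes, one of which agrees with the score. No row sets low against intact.

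**Percentages that do match a score of 6-9.** At 1+: 6-9%. At 2+: 3-4%.

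**Effect of one patient on the low cohort.** With k responders of 15, removing a responder changes the rate by k/15 - (k-1)/14 = (15-k)/210. Removing a non-responder changes it by k/14 - k/15 = k/210. The sample size section plans around a 50% response rate, so k is 7 or 8:

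- k = 7: 8/210 = 3.8 points (responder) or 7/210 = 3.3 points (non-responder).
- k = 8: 7/210 = 3.3 points (responder) or 8/210 = 3.8 points (non-responder).

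**Effect on precision.** The plan's half-width of 25 points reproduces as 1.96 x sqrt(0.25/15) = 25.3 points. With 14 patients it is 1.96 x sqrt(0.25/14) = 26.2 points.

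**The case against.** The best defence is that the score is the defined term and the percentages only explain it. The score bands appear twice with the same limits, and the second time stand alone in the paragraph that tells pathologists how to score. The indeterminate sentence itself opens with the score. Read that way, 1-2% at 2+ is low because its score is not 6-9, and 5% and 10% at 1+ are settled by the explicit limits for low and intact. This is a sensible reading and probably the intended one. It does not dispose of the point, because the plan states no precedence and the percentage sentence is also worded as a definition.

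The defence does succeed against several stronger readings that a reader might infer:

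- **3+ staining is unclassified.** It is not. The percentage text is silent on it, but the score covers it: 1% scores 3 (low), 2-3% scores 6 or 9 (indeterminate), and 4% scores 12 (intact).
- **The bands leave gaps at 5.5 or 9.5.** These arise only if the two pathologists' scores are averaged, which the plan does not say. Every whole-number score has exactly one class.
- **One patient moves the low-cohort rate by 1/15, or 6.7 points.** Removing a patient changes the denominator as well, and near 50% the shift is 3.3-3.8 points.
- **The stage 1 decision on 12 patients is exposed.** For single-intensity tumours, only exactly 10% at 1+ touches the intact cohort, and both the score and the explicit limit of at least 10% call it intact.
- **Class could be chosen once response is known.** The documents do not say when the initial batches are scored relative to response. After closure of the normal arm, tumours are analysed before enrolment.

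It is also fair that the low cohort, where the clearest conflict lies, carries no hypothesis test or stopping rule and is described as hypothesis generating.

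**Conclusion.** The point holds as an error in the classification rule as written. The percentage text does not reproduce the score band it claims to restate, and it yields a different class at 1% and 2% at 2+ and a double class at 5% and 10% at 1+. The score rule taken alone is complete and consistent for whole-number scores.

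The conflict is narrow. For single-intensity tumours it always lies between a cohort and indeterminate. A reader might infer that a tumour could swing between low and intact. That arises only with mixed staining and an assumed rule of adding across intensities: for example 4% at 1+ plus 3% at 2+ sums to 10, intact by score, while its 1+ component fits the percentage text for low. The documents do not set out how mixed staining is combined, so I do not rest the point on it.

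The documents give no distribution of scores, so the number of patients affected is unknown. Each patient removed from the low cohort moves its estimated response rate by about 3-4 points, assuming a full cohort of 15 and a rate near 50%. The correction is still needed because this variable defines the primary comparison and may decide enrolment.

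**What to change.** State in Methodology that the nuclear long score alone determines BRCA1 class, with the cut-offs the protocol already uses: 5 or less low, 6-9 indeterminate, 10 or more intact.

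Then do one of two things:

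- delete the percentage equivalents; or
- correct them to match the score, so that indeterminate reads 6-9% at 1+ or 3-4% at 2+. In that case the low entry should also take in 1-2% at 2+, which would otherwise drop out of the percentage text.

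This keeps the sponsor's own cut-offs and makes no judgement on whether they are biologically right. The cost is a few lines of protocol wording, with no new samples, readers or patients.

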## 3. Trial Design

### 3.1. Study Endpoints

**Primary Endpoint:** To correlate BRCA1 protein expression, as measured by IHC with overall response rate for metastatic breast cancer patients treated with pegylated liposomal doxorubicin. . The overall response rate is defined as the percentage of evaluable patients who achieve complete response (CR) or partial response (PR) as measured by RECIST 1.1 on CT or PET/CT as the best overall response

**Secondary Endpoint:** To correlate BRCA1 protein expression, as measured by IHC with median progression free survival for metastatic breast cancer patients treated with pegylated liposomal doxorubicin. The progression free survival is measured as the times from the start of pegylated liposomal doxorubicin to the time the patient is first recorded as having disease progression or dies.

3.2. **Study Design** This study is a prospective single arm Phase II trial to assess the association of BRCA1 protein expression with overall response rate in patients with HER2 negative metastatic breast cancer treated with pegylated liposomal doxorubicin. Patients who qualify for enrollment into the study will receive pegylated liposomal doxorubicin as a single agent intravenous at 30mg/m^2 every 21 days

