## 8. Study Statistics

8.1. **Statistical Methods:** This study is a prospective single arm Phase II trial to assess association of BRCA1 protein expression with overall response rate in patients with metastatic breast cancer on pegylated liposomal doxorubicin in patients with metastatic breast cancer. We plan to consent 50 to 60 patients with the goal of enrolling a total of 50 patients, with adequate primary tumor tissue for BRCA1 protein expression, into this study. It is estimated that 30% of patients will have low BRCA1 protein expression and therefore anticipate approximately a 35 to 15 patient split for normal BRCA1 to low BRCA1 expression status.

Recruitment and tissue analysis: Patients will be consented and after enrollment of the first 12 patients, a batch analysis of their tumors will be performed to analyze tumor BRCA1 protein expression. This will allow us to assign the patients to their respective cohorts (Normal BRCA1 protein expression and Low BRCA1 protein expression). This will be done until we have 12 patients in the normal BRCA1 protein arm. After that, an interim analysis will be performed for the normal BRCA1 arm and stopping rule will be applied as mentioned in the study design

8.2. **Analytic plan for primary objective:**

**Definition of primary endpoint:** Response rate is defined as the percentage of evaluable patients who achieve complete response (CR) or partial response (PR) as measured by RECIST on imaging as the best overall response.

**Low BRCA1 protein expression:** The number and percentage of patients falling into response category will be tabulated. The estimate of the response rate will be presented with 2-sided 95% exact binomial confidence intervals. We anticipate this data to be hypothesis generating and will form the basis for a future prospective clinical trial enrolling larger number patients to evaluate if low BRCA1 expression, as determined by IHC, is predictive of response to treatment with DNA damaging agents.

**Normal BRCA1 protein expression:** The estimate of the response rate will be presented with 2-sided 95% exact binomial confidence intervals. If 5 or fewer patients with response are observed among the 35 patients, then there will be no further investigation of the treatment. If 6 responses are observed out of 35 patients, there is 80% confidence that the true response rate >11.2%.

Interim analysis:

**Low BRCA1 protein expression:** No interim analysis will be conducted

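### The endpoints are to correlate BRCA1 expression with response and PFS, but the 0-300 score is used only to form two cohorts summarised separately, so no association with the score is estimated

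*Combined protocol and SAP*

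**What the plan says.** Section 3.1 words the primary endpoint as "To correlate BRCA1 protein expression, as measured by IHC with overall response rate", and the secondary endpoint likewise for median PFS.

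The Methodology part of section 1.2 has "Two Board Certified pathologists" evaluate each case. Staining intensity (0-3) is multiplied by the percentage of positive cells, "resulting in a values ranging from 0 to 300". A score of 5 or less is low, 10 or more is intact, and there is a middle category: "indeterminate BRCA1 expression as nuclear long score of 6-9".

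In section 8.1 the assay is run in batches after enrolment to "assign the patients to their respective cohorts (Normal BRCA1 protein expression and Low BRCA1 protein expression". Section 8.2 gives a response rate with an exact 95% interval in each cohort, plus the Simon rule for the normal cohort. Section 8.3 gives Kaplan-Meier median PFS in each cohort. The low-cohort data are described as hypothesis generating and as the basis for a larger trial.

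**The concern.** The planned analyses do not deliver the stated endpoints. A graded measurement is taken on every case, yet it only sorts patients. There is no correlation, regression, trend or alternative cut-off. Patients scoring 6-9 can be enrolled and treated, because the assay follows enrolment, but section 8 gives them no place.

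The documents offer limited support for the cut-offs. The preliminary outcome data are 2/8 against 6/13 recurrences, reported by class only. The reference number attached to the low cut-off leads, in the bibliography, to a review of the drug; that may be a numbering slip, but it leaves the origin of the cut-off undocumented.

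At stake is what the next trial inherits. If response falls gradually with expression, or changes at a score above 10, some likely responders sit in the normal cohort and the contrast shrinks. The planned output could not show this.

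**Working it through.** **1. The plan's own figures.** These reproduce, and each concerns a single cohort.
- Simon design (stop at 1 or fewer of 12; positive at 6 or more of 35): the sum over x = 2 to 12 of P(X1 = x) × P(X2 ≥ 6 − x), with X1 ~ Bin(12, p) and X2 ~ Bin(23, p), gives 0.0977 at p = 0.10 and 0.9014 at p = 0.30. Both meet the stated limits.
- Low cohort: 1.96 × √(0.5 × 0.5/15) = 0.253, matching ±25%.

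The documents state no figure for a between-cohort comparison or for the score.

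**2. Share of the scale in one class.** (300 − 10)/300 = 96.7%.

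**3. What small numbers alone would do.** No comparison is planned, so a two-sided 5% Fisher test is assumed. Exact power at 15 v 35 with 50% response in the low cohort:

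| Normal-cohort response | Power |
|---|---|
| 10% | 85% |
| 20% | 54% |
| 25% (the drug's rate quoted in the protocol) | 37% |
| 30% | 23% |

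With a correct cut-off and 50% v 25%, such a test misses the difference 1 − 0.37 = 63% of the time.

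**4. Two classes against the score, fixed N = 50.** Assumptions: 30% of patients are low, and response depends on the percentile u of the score. There were 4,000 runs, with simulation error about ±1.5 points. Fisher compares low with normal; the Mann-Whitney test compares scores of responders and non-responders in all 50. The gradient is logit p = −0.807 − 2.303(u − 0.5), calibrated to average 50% in the low group and 25% in the rest. For the break at the 60th percentile (50% below, 12.5% above), the normal cohort's rate is (0.30 × 0.50 + 0.40 × 0.125)/0.70 = 28.6%.

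| Assumed truth | Fisher v rank | Same, 10% indeterminate left out of Fisher |
|---|---|---|
| No association (30% throughout) | 2.7% v 4.5% | 3.6% v 5.0% |
| Step at the plan's cut-off, 50% v 25% | 36% v 27% | 32% v 28% |
| Smooth gradient | 34% v 53% | 39% v 54% |
| Break at 60th percentile | 25% v 64% | 33% v 64% |

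Part of each gap is Fisher's conservatism, visible in the first row.

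**5. Score-scale scenarios, with and without the stage 1 stop.** The fixed-N runs assume 30% at 0-5, 5% at 6-9 and 65% at 10-300; the runs with the stop apply the Simon stage 1 rule to the normal cohort. There were 3,000 runs per fixed-N scenario. Scores of 10 or more are either uniform or, as one illustrative alternative, skewed toward low values. Entries are Fisher v rank.

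| Assumed truth | Shape | Fixed N = 50 | With stop |
|---|---|---|---|
| Linear fall, 50% at 0 to 2% at 200 or more | uniform | 56% v 88% | 66% v 81% |
| | skewed | 21% v 50% | 24% v 46% |
| Break at 50, 45% v 12% | uniform | 49% v 63% | 51% v 53% |
| | skewed | 21% v 53% | 33% v 55% |
| Plan's cut-off right, 50% v 14% | either | 68-69% v 57% | 71% v 53-55% |

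The stop matters. At a true 14%, P(1 or fewer of 12) = 0.86^12 + 12 × 0.14 × 0.86^11 = 0.48. After a stop, section 8.2 enrols low-expression patients only, leaving about 15 + 12 = 27 classified patients and a narrow spread of scores.

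**The case against.** The strongest reply is that the objective and hypothesis concern low expression. The categories are fixed in advance with a buffer zone, and the Simon rule needs cohorts. That stands, and it is why the cohorts should stay.

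The cut-offs are also not without support. The assay is described as validated, and the 43% low rate in triple-negative tumours is said to agree with DNA- and RNA-based series. The remark that "there is currently no standardized definition" refers to a BRCA1-like signature across several methods, not to this assay's threshold. The documents therefore do not show that the cut-off is wrong, only that the plan never examines it.

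A reader might infer that a null result could not be told from a misplaced cut-off. The documents do not support that. No low-versus-normal test is planned, so a null result on association is undefined, and small numbers explain a miss equally well (step 3). The missing comparison is a larger, separate gap.

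A reader might also infer that the score should replace the classes. It should not: it loses power when the plan's cut-off is right, and its advantage nearly vanishes in one scenario once the stage 1 stop is applied.

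**Conclusion.** The concern holds in a limited form. The endpoints promise a correlation, a score is generated for each case, and sections 8.2 and 8.3 estimate no association with it. An apparent lack of difference could reflect a graded relation, a break elsewhere on the scale, or small numbers, and the plan cannot examine the first two.

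The size is uncertain because the documents give no score distribution. Where the relation is graded or breaks higher up, the score's gain over a two-class test ranges from about 2 points (uniform scores, break at 50, with the stop) to 39 points (break at the 60th percentile, fixed N). Where the plan's cut-off is right at 50% v 14%, the score has about 53-57% power against 68-71%. These figures assume a two-sided 5% test that the plan does not contain, and should be read as a range.

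The point does not affect the Simon decision or the cohort intervals. Nor would a score analysis in about 50 patients settle a cut-off: a rank test, ROC area or Cox slope measures monotone association and does not locate a threshold.

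**What to change.** Keep the cohort analyses and the Simon rule unchanged. Add to sections 8.2 and 8.3, labelled exploratory and supportive:

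- **Population:** all enrolled, treated patients with a score and an outcome, including scores 6-9. Patients assayed but not enrolled after the normal cohort closes have no study outcome and are not included.
- **Score:** the recorded score, or the mean if each reader's score is recorded. The Methodology does not say whether two separate scores are kept, so state which applies.
- **Response:** a two-sided rank test of score by response, with the area under the ROC curve and its 95% interval.
- **PFS:** a Cox model on log(score + 1), with the hazard ratio and 95% interval.
- **Cut-off:** response shown by score, as a plot or in a few prespecified bands, as descriptive input to the next trial's choice.

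The cost is a few sentences in section 8 and a few hours of analysis, with no extra patients or assays. The downside is lower power than a two-class comparison if the plan's cut-off is right, and a possibly smaller gain if the normal cohort stops early. That is why both analyses should be reported.
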